### **Safety Criteria for Dose Adjustment or Stopping Treatment:**

If, at any time during the study, a subject meets 1 or more of the clinical or laboratory exclusion criteria for the study (eg, seated SBP  $\geq$  175 mmHg or DBP  $\geq$  100 mmHg, serum potassium  $>$  5.2 mEq/L, serum cortisol  $<$  3 mcg/dL), laboratory test values will be confirmed using a local lab and BP measurements will be repeated. If laboratory exclusion criteria are met, the subject's dose of study drug may be temporarily withheld, adjusted, or stopped by the investigator in consultation with the medical monitor. The subject will receive appropriate antihypertensive treatment if clinically indicated, and will remain in the study for further safety monitoring. Guidelines for dose adjustment/stopping in the management of hyperkalemia are included in **Section 6.5.1**. All subjects will be given dietary counseling to avoid foods high in potassium during the study ([Appendix 12.6](#)). Guidelines for the management of hypotension are included in **Section 0**. In addition, serum cortisol levels will be monitored throughout the study, and all subjects will be monitored for signs and symptoms of adrenal insufficiency (ie, nausea, vomiting, light-headedness, low BP, or electrolyte abnormalities) at every study visit. Based on changes in cortisol levels, an adrenocorticotropic hormone (ACTH) stimulation test ([Appendix 12.7](#)) may be

performed and the subject's dose of study drug may be stopped. Guidelines for potential dose discontinuation in the management of adrenal insufficiency are included in [Section 6.5.3](#).

Subjects who wish to stop treatment for any reason may stop at any time during the study. If the study treatment is permanently discontinued, the subject will remain in the study to complete all study assessments as described in the schedule of assessments (SoA) ([Table 1](#) and Table 2) through Study Week 8 (end-of-treatment visit). Subjects should also be encouraged to return for a final follow-up visit 4 weeks after the Study Week 8 visit for Part 1 and 2 weeks after the Study Week 8 visit for Part 2, at which the end-of-study assessments will be performed.

An overview of the study design is presented in the Study Schema ([Figure 1](#)). Safety and efficacy assessments and study procedures are outlined in the SoA ([Table 1](#) and Table 2). Detailed descriptions of study assessments are provided in [Section 4.8](#) and [Section 8](#).

## 4.2. Scientific Rationale for Study Design

The objective of Part 1 of the Phase 2 study is to evaluate both QD and BID dosing across a total daily dose of 12.5 mg to 100 mg for 8 weeks of treatment to determine at which doses substantial reductions in blood pressure occur and to determine if there is a dose response on BP with increasing doses. The dose range chosen was based on the Phase 1 study findings, and is considered to be a wide enough dose range to examine whether a dose-dependent response on BP could be observed. Further, we are interested in determining if BID dosing may be a better dosing regimen to sustain reductions in aldosterone over a 24-hour period, reduce any concomitant rise in trough aldosterone levels, and ultimately lead to a greater reduction in BP in patients. The examination of PK, PD (eg, aldosterone concentration), and BP at the doses proposed should enable a better understanding of dose requirements to be further examined in subsequent trials.

The key efficacy endpoints, both primary and secondary, were selected to assess the changes in BP from baseline with treatment. The treatment period of 8 weeks was considered sufficient to assess the maximum effect on BP for a given dose and to assess safety. The assessment of BP, assessing changes in both systolic and diastolic BP, has been standard for previous BP trials with novel therapeutics.

Data obtained from the interim analyses performed in Part 1 of the study will be used to inform Part 2.

## 4.3. Number of Subjects/Number of Centers

Approximately 1100 subjects will undergo up to 2 weeks of pre-Screening. For Part 1, it is estimated that approximately 270 subjects will have qualifying PRA and serum aldosterone levels to be eligible to enter Screening/start of Placebo Run-in, and (assuming an approximately 40% screen failure rate) a total of approximately 160 subjects will meet all eligibility requirements to qualify for enrollment in Part 1 of the study. The subjects who qualify for enrollment will be randomly divided into 4 equal treatment groups (1:1:1:1 with approximately 30 subjects per group, stratified by BP, ie, seated SBP  $\leq$  160 mmHg and seated SBP  $>$  160 mmHg) across approximately 50 study centers in the United States.

For Part 2, it is estimated that approximately 60 subjects will have qualifying PRA and serum aldosterone levels to be eligible to enter Screening/start of Placebo Run-in, and (assuming an approximately 40% screen failure rate) a total of 36 subjects will meet all eligibility

requirements to qualify for enrollment in Part 2 of the study. The subjects who qualify for enrollment will be randomized (5:1) to either 100 mg QD MLS-101 or placebo such that the MLS-101 treatment group will consist of approximately 30 subjects and the placebo treatment group will consist of approximately 6 subjects across approximately 10 study centers in the United States.

#### **4.4. Study Duration**

It is anticipated that each subject's duration of participation in Part 1 will be approximately 16 weeks (up to 2 weeks of pre-Screening followed by up to 2 weeks of a Screening/single-blind Placebo Run-in period, 8 weeks of double-blind treatment with study drug, and a 4-week follow-up period). For Part 2, subject's duration of participation will be approximately 16 weeks (up to 4 weeks of pre-Screening, followed by up to 2 weeks of a Screening/single-blind Placebo Run-in period, 8 weeks of double-blind treatment with study drug, and a 2-week follow-up period). Total duration of the study will be approximately 21 months which includes periods for site activation, subject recruitment, treatment, and follow-up.

The doses that are evaluated in this study will inform dose selection for further study in a randomized, double-blind, active-controlled Phase 2/3 study.

#### **4.6. End of Study Definition**

The end of study is defined as the date of the last visit of the last participant in the study. A participant is considered to have completed the study if he/she has completed all periods of the study including Visit 16 (end-of-study visit) at Study Week 12 and Study Week 10 for Parts 1 and 2, respectively.

At the time of study completion or early discontinuation, subjects will be queried regarding any AEs, concomitant medications, and concurrent procedures, which will be recorded on the appropriate page(s) of the source documents and electronic case report form (eCRF). At the final study visit, subjects with ongoing AEs that are considered by the investigator to be serious, study drug-related, or associated with the target area will be requested to continue to follow up with the investigator until the AE resolves, is stable, or follow-up is no longer possible/necessary. Any death that occurs while on study or within 30 days (Part 1) and 15 days (Part 2) after the subject's last dose of study drug must be reported to the sponsor/designee for the study within 24 hours after the center becomes aware of the event.

#### **4.7. Criteria for Study Termination**

Both the sponsor and the investigator reserve the right to terminate the study according to the study contract. The sponsor may issue a protocol amendment or discontinue the study entirely, based on regulatory authority or IRB/Independent Ethics Committee (IEC) recommendations, drug safety or availability concerns, discontinuation of the development program for MLS-101, or at the sponsor's discretion with at least 30 days' notice. The DSMB may also recommend study termination based on a review of the safety data.

#### **4.8. Study Conduct**

A schedule of study assessments is presented in [Table 1](#). Details of study assessments are provided in [Sections 4.8.1 to 4.8.15](#) and [Section 8](#). Subjects should be in a fasted state for all study visits in Part 2 unless there is a medical reason not to fast as determined by the investigator.

##### **4.8.1. Pre-Screening (Visit 1, Study Days -28 to -14 for Part 1 or -42 to -14 for Part 2)**

Subjects with a history of hypertension, ie, SBP  $\geq$  135 mmHg, who meet the protocol definition for stable background treatment defined as  $\geq$  2 antihypertensives (note: a combination pill = 2 antihypertensives) that have been stable at their prescribed doses for at least 4 weeks prior to signing the pre-Screening informed consent will enter up to 2 weeks of pre-Screening for Part 1 and 4 weeks of pre-Screening for Part 2 upon completion of the IRB-approved pre-Screening informed consent and the following procedures will be performed:

- Review medical history
- Vital signs (body temperature, heart rate, respiratory rate)
- AOBP (average of the last 2 of 5 unattended measurements using an automated oscillometric sphygmomanometer device after approximately 5 minutes of rest in the seated position)

- Blood draw – blood samples for aldosterone and PRA to be collected in the morning after at least 8 hours of fasting

#### **4.8.2. Screening/Start of Placebo Run-in (Visit 2/Visit 3, Study Day -14 ± 2 Days)**

All subjects with PRA and serum aldosterone values meeting the pre-Screening criteria (ie, PRA  $\leq$  1 ng/mL/h and aldosterone  $\geq$  1 ng/dL for Part 1; PRA  $>$  1 ng/mL/h and aldosterone  $\geq$  1 ng/dL for Part 2; or alternative target guidance provided by the sponsor) will be eligible to enter Screening/Placebo Run-in. The investigator (or appropriate delegate at the investigator site) will obtain Screening informed consent from each subject and the following procedures will be performed:

- Inclusion/exclusion assessment
- Review medical history
- Physical examination
- Vital signs (body temperature, heart rate, respiratory rate)
- AOBP (average of the last 2 of 5 unattended measurements using an automated oscillometric sphygmomanometer device after approximately 5 minutes of rest in the seated position)
- Standing BP assessment ([Appendix 12.5](#))
- Standard 12-lead electrocardiogram (ECG); ECG changes consistent with hyperkalemia will require confirmation of potassium levels at a local laboratory
- Pregnancy test (serum; women of childbearing potential only; follicle stimulating hormone to confirm postmenopausal status in postmenopausal women)
- Blood draw ([Table 6](#))
  - Blood samples for aldosterone, cortisol, 11-deoxycorticosterone, 11-deoxycortisol, and PRA will be collected.
  - Blood samples for hematology, chemistry, and coagulation tests (coags) will be collected, including hemoglobin A1c concentration and ACTH
  - Blood samples for ACTH stimulation test ([Appendix 12.7](#))
- ACTH stimulation test (may be waived with sponsor's approval)
- Urine collection for urinalysis ([Table 6](#))
- Review of concomitant medications

Once all Screening procedures are complete, subjects immediately enter the single-blind run-in period of BID (Part 1) or QD (Part 2) oral treatment with placebo while continuing to remain on stable doses of their background antihypertensive medications.

#### **4.8.3. Single-blind Placebo Run-In Week 2 (Visit 4, Study Day -7 ± 2 Days)**

Subjects will return to the research facility at the beginning of Week 2 of the run-in period for the following procedures:

- Inclusion/exclusion assessment (based on Screening assessment results from V2/V3). If Screening results are available, and subject is determined to be ineligible for the study, the site will review AEs, concomitant medications, and study drug compliance. Vital signs and AOBP will not be performed.
- Vital signs (body temperature, heart rate, respiratory rate) only if subject is eligible for the study or if Screening results are not yet available

- AOBP (average of the last 2 of 5 unattended measurements using an automated oscillometric sphygmomanometer device after approximately 5 minutes of rest in the seated position) only if subject is eligible for the study or if Screening results are not yet available
- Review of AEs, concomitant medications, and study drug compliance for all subjects regardless of eligibility status

Subjects will be evaluated for eligibility based on Screening results and if eligible, or if Screening results are not available, subjects will continue on Week 2 of Placebo Run-in and will be given an ABPM device and instructions on how to perform the ABPM procedure by the investigator to take home for use on Study Day 0, approximately 24 hours before Randomization (Study Day 1). Note: only subjects who have Screening results and are considered eligible should be provided with the ABPM for home use. Subjects who do not have Screening results available should attend Visit 5. In addition, subjects will be given either a spot urine collection kit for Part 1 or a 24-hour urine collection kit for Part 2 to take home for use on Study Day 1. In Part 1 of the study, first morning urine will be collected prior to morning dose of study drug on Study Day 1 and again at the end of Study Week 8 (ie, Study Day  $56 \pm 2$  or end-of-treatment period) for determination of potassium, sodium, and creatinine levels. In Part 2 of the study, 24-hour urine collection will be performed on Study Day 1 and again at the end of Study Week 4 (ie, Visit 10, Study Day  $28 \pm 2$ ) for determination of potassium, sodium, creatinine, and aldosterone levels.

#### **4.8.4. Telephone or Office Visit (Visit 5, Study Day 0)**

After completion of the single-blind, Placebo Run-in period, subjects will participate in a telephone or office visit on Study Day 0 in which they will be reminded how to perform the ABPM and spot urine collection procedures by the investigator or study coordinator. If Screening results were not available at Placebo Run-in Visit 4, subjects should participate in an office visit to review eligibility. If eligible, ABPM procedure will be initiated. The following procedures will be performed:

- Inclusion/exclusion assessment (if necessary)
- 24-hour ABPM

#### **4.8.5. Randomization/Baseline (Visit 6, Study Day 1)**

After first morning spot (Part 1) or 24-hour (Part 2) urine collection at home, subjects will return to the clinic on Study Day 1 (morning visit), and those who continue to meet all eligibility requirements will be randomized to MLS-101 or placebo and the following procedures performed prior to administration of the initial morning dose of study drug:

- Inclusion/exclusion assessment
- Physical examination
- Vital signs (body temperature, heart rate, respiratory rate)
- AOBP (average of the last 2 of 5 unattended measurements using an automated oscillometric sphygmomanometer device after approximately 5 minutes of rest in the seated position)
- Standing BP assessment ([Appendix 12.5](#))
- Spot urine collection (**Part 1 only**)
- 24-hour urine collection (**Part 2 only**)

- Standard 12-lead ECG; ECG changes consistent with hyperkalemia will require confirmation of potassium levels at a local laboratory
- Pregnancy test (urine; women of childbearing potential only)
- Blood draw ([Table 6](#))
  - Blood samples for aldosterone, cortisol, 11-deoxycorticosterone, 11-deoxycortisol, and PRA will be collected
  - Blood samples for hematology, chemistry, and coags will be collected, including hemoglobin A1c concentration and ACTH
  - Single blood samples for determination of MLS-101 will be collected. Additional blood samples for long-term storage for metabolites, drug-drug interaction profiles of background therapy, or other exploratory analyses will also be collected.
  - Serial PK sampling – if subject consents to additional blood draws, blood samples for determination of MLS-101 (and metabolites) are to be collected predose, and 1, 2, 3, and 4 hours postdose.
- Urine collection for urinalysis ([Table 6](#))
- Review of AEs, concomitant medications, and study drug compliance

#### **4.8.6. Study Week 1 (Visit 7, Study Day 7 ± 2 Days)**

On Study Day 7 ± 2 days, subjects will return to the site and the following procedures will be performed prior to site administration of the morning dose of study drug:

- Vital signs (body temperature, heart rate, respiratory rate)
- AOBP (average of the last 2 of 5 unattended measurements using an automated oscillometric sphygmomanometer device after approximately 5 minutes of rest in the seated position)
- Standing BP assessment ([Appendix 12.5](#))
- Blood draw ([Table 6](#))
  - Blood samples for hematology, chemistry, and coags will be collected, including hemoglobin A1c concentration, cortisol, and ACTH
  - Single blood samples for determination of MLS-101 will be collected. Additional blood samples for long-term storage for metabolites, drug-drug interaction profiles of background therapy, or other exploratory analyses will also be collected.
- Urine collection for urinalysis ([Table 6](#))
- Review of AEs, concomitant medications, and study drug compliance

#### **4.8.7. Study Week 2 (Visit 8, Study Day 14 ± 2 Days)**

On Study Day 14 ± 2 days, subjects will return to the site and the following procedures will be performed prior to site administration of the morning dose of study drug:

- Vital signs (body temperature, heart rate, respiratory rate)
- AOBP (average of the last 2 of 5 unattended measurements using an automated oscillometric sphygmomanometer device after approximately 5 minutes of rest in the seated position)
- Blood draw - blood samples for hematology, chemistry, and coags will be collected, including hemoglobin A1c concentration, cortisol, and ACTH ([Table 6](#))
- Urine collection for urinalysis ([Table 6](#))

- Review of AEs, concomitant medications, and study drug compliance

#### **4.8.8. Study Week 3 (Visit 9, Study Day 21 ± 2 Days)**

On Study Day 21 ± 2 days, subjects will return to the site and the following procedures will be performed prior to site administration of the morning dose of study drug:

- Vital signs (body temperature, heart rate, respiratory rate)
- AOBP (average of the last 2 of 5 unattended measurements using an automated oscillometric sphygmomanometer device after approximately 5 minutes of rest in the seated position)
- Blood draw – blood samples for hematology, chemistry, and coags will be collected, including hemoglobin A1c concentration, cortisol, and ACTH ([Table 6](#))
- Urine collection for urinalysis ([Table 6](#))
- Review of AEs, concomitant medications, and study drug compliance

#### **4.8.9. Study Week 4 (Visit 10, Study Day 28 ± 2 Days)**

On Study Day 28 ± 2 days, subjects will return to the site and the following procedures will be performed prior to site administration of the morning dose of study drug:

- Vital signs (body temperature, heart rate, respiratory rate)
- AOBP (average of the last 2 of 5 unattended measurements using an automated oscillometric sphygmomanometer device after approximately 5 minutes of rest in the seated position)
- Initiate 24-hour ABPM (**Part 2 only**)
- 24-hour urine collection (**Part 2 only**)
- Blood draw ([Table 6](#))
  - Blood samples for aldosterone, cortisol, 11-deoxycorticosterone, 11-deoxycortisol, and PRA will be collected
  - Blood samples for hematology, chemistry, and coags will be collected, including hemoglobin A1c concentration and ACTH
  - Single blood samples for determination of MLS-101 will be collected. Additional blood samples for long-term storage for metabolites, drug-drug interaction profiles of background therapy, or other exploratory analyses will also be collected.
  - Serial PK sampling – if subject consents to additional blood draws, blood samples for determination of MLS-101 (and metabolites) are to be collected predose, and 1, 2, 3, and 4 hours postdose.
- Urine collection for urinalysis ([Table 6](#))
- Pregnancy test (urine; women of childbearing potential only)
- Review of AEs, concomitant medications, and study drug compliance

#### **4.8.10. Study Week 5 (Visit 11, Study Day 35 ± 2 Days)**

On Study Day 35 ± 2 days, subjects will return to the site and the following procedures will be performed prior to site administration of the morning dose of study drug:

- Vital signs (body temperature, heart rate, respiratory rate)
- AOBP (average of the last 2 of 5 unattended measurements using an automated oscillometric sphygmomanometer device after approximately 5 minutes of rest in the seated position)

- Blood draw – blood samples for hematology, chemistry, and coags will be collected, including hemoglobin A1c concentration, cortisol, and ACTH ([Table 6](#))
- Urine collection for urinalysis ([Table 6](#))
- Review of AEs, concomitant medications, and study drug compliance

#### **4.8.11. Study Week 6 (Visit 12, Study Day 42 ± 2 Days)**

On Study Day 42 ± 2 days, subjects will return to the site and the following procedures will be performed prior to site administration of the morning dose of study drug:

- Vital signs (body temperature, heart rate, respiratory rate)
- AOBP (average of the last 2 of 5 unattended measurements using an automated oscillometric sphygmomanometer device after approximately 5 minutes of rest in the seated position)
- Blood draw – blood samples for hematology, chemistry, and coags will be collected, including hemoglobin A1c concentration, cortisol, and ACTH ([Table 6](#))
- Urine collection for urinalysis ([Table 6](#))
- Review of AEs, concomitant medications, and study drug compliance

#### **4.8.12. Study Week 7 (Visit 13, Study Day 49 ± 2 Days)**

On Study Day 49 ± 2 days, subjects will return to the site and the following procedures will be performed prior to site administration of the morning dose of study drug:

- Vital signs (body temperature, heart rate, respiratory rate)
- AOBP (average of the last 2 of 5 unattended measurements using an automated oscillometric sphygmomanometer device after approximately 5 minutes of rest in the seated position)
- Initiate 24-hour ABPM
- Blood draw – blood samples for hematology, chemistry, and coags will be collected, including hemoglobin A1c concentration, cortisol, and ACTH ([Table 6](#))
- Urine will be collected for urinalysis ([Table 6](#))
- Review of AEs, concomitant medications, and study drug compliance

#### **4.8.13. Study Week 8 (Visit 14, Study Day 56 ± 2 Days)**

At the Study Week 8 visit (Visit 14), subjects will begin 24-hour ABPM procedure. On Study Day 56 ± 2 days, subjects will return to the site and the following procedures will be performed prior to site administration of the morning dose of study drug:

- Physical examination
- Vital signs (body temperature, heart rate, respiratory rate)
- AOBP (average of the last 2 of 5 unattended measurements using an automated oscillometric sphygmomanometer device after approximately 5 minutes of rest in the seated position)
- Standing BP assessment ([Appendix 12.5](#))
- Repeat 24-hour ABPM if procedure at Study Week 7 deemed a failure
- Spot urine collection (**Part 1 only**)
- Standard 12-lead ECG; ECG changes consistent with hyperkalemia will require confirmation of potassium levels at a local laboratory
- Pregnancy test (urine; women of childbearing potential only)
- Blood draw ([Table 6](#))

- Blood samples for hematology, chemistry, and coags will be collected, including hemoglobin A1c concentration, cortisol, and ACTH
- Single blood samples for determination of MLS-101 will be collected. Additional blood samples for long-term storage for metabolites, drug-drug interaction profiles of background therapy, or other exploratory analyses will also be collected.
- Blood samples for ACTH stimulation test ([Appendix 12.7](#))
- ACTH stimulation test (may be waived with sponsor's approval)
- Urine collection for urinalysis ([Table 6](#))
- Review of AEs, concomitant medications, and study drug compliance

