##### **3.2.2. Secondary Efficacy Endpoints**

- Change in 24-hour ambulatory blood pressure monitoring (ABPM) parameters (systolic and diastolic) from baseline to the end of Study Week 7 (ie, Study Day 49 ± 2)
- Change in office-measured (average of last 2 of 5 unattended measurements using an automated oscillometric sphygmomanometer device after approximately 5 minutes of rest in the seated position) SBP and diastolic blood pressure (DBP) from baseline to the end of Study Weeks 1, 2, 3, 4, 5, 6, and 7 (± 2 days); change in office-measured DBP from baseline to the end of Study Week 8 (ie, Study Day 56 ± 2 or end-of-treatment period)
- Proportion of subjects who achieve in office-measured BP of ≤ 130/80 mmHg by the end of Study Week 8 (ie, Study Day 56 ± 2 or end-of-treatment period)

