#### 6.1.2. Dosing and Administration

*Placebo Run-In:* In Part 1, upon signing the Screening/main study ICF, subjects will begin a single-blind (subjects blinded to treatment allocation), up to 2-week run-in period of BID oral treatment with placebo, while continuing to remain on stable doses of their background antihypertensive medications. Subjects will orally administer placebo morning and evening, approximately 12 hours apart. On site visit days, subjects should be instructed to take their morning dose of study drug at the site. In Part 2, upon signing the Screening/main study ICF, subjects will begin a single-blind (subjects blinded to treatment allocation), up to 2-week run-in period of QD oral treatment with placebo, while continuing to remain on stable doses of their background antihypertensive medications.

*8-Week Treatment Period:* In Part 1, subjects will orally administer the assigned study drug (MLS-101 [25 mg BID, 50 mg QD, 100 mg QD] or placebo) according to the assigned dosing regimen for 8 weeks beginning on Study Day 1. To maintain the integrity of the blind, all subjects (regardless of dosing group) will orally administer study drug morning and evening, approximately 12 hours apart; active drug is administered as the morning dose for all QD dose groups. Subjects will be monitored by ABPM for 24 hours before the first morning dose on Study Day 1 and for 24 hours after the morning dose on Study Day  $49 \pm 2$  days (end of Week 7). On site visit days, subjects should be instructed to take their morning dose of study drug at the site. In Part 2, subjects will orally administer the assigned study drug (MLS-101 [100 mg QD] or placebo) according to the assigned dosing regimen for 8 weeks beginning on Study Day 1. Subjects will be monitored by ABPM for 24 hours before the first morning dose on Study Day 1, for 24 hours beginning on Study Day  $28 \pm 2$  days (Week 4), and for 24 hours after the morning dose on Study Day  $49 \pm 2$  days (end of Week 7).

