### **8.1.2. 24-hour Ambulatory Blood Pressure Monitoring**

Subjects will be monitored by ABPM for 24 hours before the first dose on Study Day 1 and before the first dose on Study Day  $49 \pm 2$  days (end of Week 7) according to the method described in the AHA scientific statement on measuring BP in humans ([Muntner 2019](#)). Blood pressure will be measured automatically every 15 to 30 minutes for a 24-hour period using an ABPM device provided to each site by the central BP laboratory or the sponsor for the duration of the study. The ABPM data will be electronically transferred to the central BP laboratory and subsequently to the contract research organization. Details on ABPM procedure (installation, recording, and transfer of data), including subject preparation, will be provided in the BP manual. At the second clinic visit of the Placebo Run-in period (Visit 4), subjects will be given an ABPM device and instructions by the investigator on how to perform the ABPM procedure at home. Subjects will participate in a telephone visit on Study Day 0 (Visit 5) in which they will be reminded of the instructions on how to perform the ABPM procedure at home by the investigator or study coordinator. The ABPM procedure will be initiated at home approximately 24 hours before Randomization (Study Day 1) and again in the clinic at the end of Study Week 4 (ie, Visit 10, Study Day  $28 \pm 2$ ) in Part 2 and Study Week 7 (ie, Visit 13; Study Day  $49 \pm 2$ ) in Parts 1 and 2. Alternatively, sites may choose to schedule an office visit on Study Day 0 (Visit 5) to initiate the ABPM procedure (the ABPM procedure will be initiated in the clinic at Study Weeks 4 and 7 unless a subject is not able to attend the visit due to extraordinary circumstances, such as COVID-19 restrictions including site closure, subject exposure to COVID-19, or subject testing positive for COVID-19). If, for any reason, the ABPM procedure is deemed a failure at the end of Study Week 7, it can be repeated at Study Week 8. Training for the ABPM procedure can be done at an office visit or via phone.

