6.4.2 Secondary Efficacy Outcome Analyses

All secondary efficacy endpoints analyses will be considered supportive and any inferential statistics will be considered descriptive in nature. No adjustment for multiplicity will be performed. Unless otherwise stated, all secondary efficacy endpoints analyses will be based on the FAS.

6.4.2.1 24-hour ABPM

The ABPM will be measured in the clinic at baseline and end of treatment (EOT). If, for any reason, the ABPM procedure is deemed a failure, it can be repeated, and therefore no imputation will be employed regardless of use of rescue medications. The last available post-baseline ABPM assessment will be considered as EOT.

Additionally, ABPM is also collected at the end of Study Week 4 in Part 2. If a repeat test is performed, it supersedes the original test results for Week 4. Tests denoted as Week 4 cannot be flagged as EOT, even if no later post-baseline assessment exists.

The ABPM measurements will be included regardless of the QC Status of individual readings or the derived variables. QC statuses of 'Failed' will be noted in the listings.

Specific derived variables based on ABPM measurements include mean 24-hour, mean Daytime, and mean Nighttime of SBP, DBP, and heart rate. Mean 24-hour Mean Arterial Pressure is derived as

$$(\text{mean 24-hour SBP} + \text{mean 24-hour DBP})/2$$

Each of these derived variables will be summarized by treatment group and visit using descriptive statistics.

Change from baseline to EOT in 24-hour mean SBP (and DBP) based on ABPM will be analyzed using an ANCOVA with a term for treatment group and a baseline mean 24-hour value as a covariate.

The nighttime dip is defined as

$$100\% \times (\text{mean daytime SBP} - \text{mean nighttime SBP}) / \text{mean daytime SBP}$$

It is expressed as a percentage and will be summarized by treatment group and visit using descriptive statistics. In addition, the number and percentage of subjects with nighttime dip in each of the dipper categories (Bloomfield & Park, 2015) will be presented by treatment group and visit.

The categories are:

- < 10%
- 10-20% inclusive
- > 20%

All ABPM variables will be listed.

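### Protocol 4.8.13 contradicts itself on whether ABPM is started at Week 8, and the SAP's last-session rule would let a Week 8 recording replace a valid Week 7 one

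*Protocol*

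**What the plan says.** Protocol 3.2.2 lists as its first secondary efficacy endpoint the change in ABPM "parameters (systolic and diastolic) from baseline to the end of Study Week 7". Section 4.8.12 (Visit 13, Day 49 ± 2) carries the instruction "Initiate 24-hour ABPM".

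Section 4.8.13 (Visit 14, Day 56 ± 2) opens with "At the Study Week 8 visit (Visit 14), subjects will begin 24-hour ABPM procedure". Its bullet list then has "Repeat 24-hour ABPM if procedure at Study Week 7 deemed a failure". Section 8.1.2 and footnote i of Tables 1 and 2 agree with the bullet: Week 8 is a repeat for a Week 7 session that failed.

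SAP 6.4.2.1 states "The last available post-baseline ABPM assessment will be considered as EOT". It bars a Part 2 Week 4 session from being used as end of treatment, and it includes ABPM data irrespective of QC status. SAP section 7 says that the collected data mix Weeks 7 and 8 because Amendment 4 moved the recording. It renames the endpoint as end of treatment and says that the week depends on the protocol under which the subject enrolled.

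Two sections disagree on the timing of the Week 7 recording; the visit meant in both is Visit 13. Protocol 6.1.2 has it run "for 24 hours after the morning dose on Study Day", while 8.1.2 opens with "Subjects will be monitored by ABPM for 24 hours before the first dose on Study Day 1 and before the first dose on Study Day".

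**The concern.** A site that works from the first sentence of 4.8.13 records at Week 8 subjects who already have a good Week 7 recording. The SAP rule then discards the recording made at the protocol's own endpoint week. The rule does not ask whether Week 7 failed. Because QC status plays no part in selection, a Week 8 session that failed QC could displace a Week 7 session that passed.

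What is at stake is which recording enters the ABPM ANCOVA for some subjects. That choice would depend on how a site read one sentence, and the SAP does not say that it can happen.

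**Working it through.** The plan gives no precision figure for ABPM. Its one precision figure is for office SBP, and it reproduces: 1.645 × 9 × √(2/30) = 3.82, against the stated ± 3.8. It has no bearing here, so the check is a comparison of texts.

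**Step 1: what the protocol says about ABPM at Week 8**

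| Place | ABPM at Week 8 |
|---|---|
| 4.8.13, first sentence | Started, no condition |
| 4.8.13, bullet | Only if Week 7 failed |
| Footnote i, Tables 1 and 2 | Only if Week 7 failed |
| 8.1.2 | Only if Week 7 failed |
| 3.2.2 and 4.8.12 | Endpoint and start of recording are at Week 7 |

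One sentence stands against all the rest. It fits the schedule that SAP section 7 says applied before Amendment 4.

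**Step 2: what the SAP rule selects**

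| Subject | Session taken as EOT | Acceptable? |
|---|---|---|
| A. Earlier schedule, recorded at Week 8 | Week 8 | Yes; disclosed in SAP section 7 |
| B. Week 7 schedule, valid Week 7 only | Week 7 | Yes |
| C. Week 7 schedule, Week 7 failed, repeated at Week 8 | Week 8 | Yes; the protocol's intended repeat |
| D. Week 7 schedule, valid Week 7, also recorded at Week 8 | Week 8 | No; valid Week 7 session lost |

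Only case D is affected.

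**Step 3: whether the SAP covers case D.** Section 7 ties the week to protocol version. Case D arises within the current version, so that explanation does not reach it. In Part 2 this is plain: the cohort came in with Amendment 5 (SAP 2.5.2), after Amendment 4 had moved ABPM to Week 7, so protocol version cannot account for any Week 8 session there. SAP 9.2 says that a repeat replaces a missing ABPM, which fits case C but does not limit the last-available rule. For Week 4 the SAP does say which test counts when there are two. For Week 7 against Week 8 it does not.

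**Step 4: the distance between the two sessions.** Nominally 56 − 49 = 7 days. With the ± 2-day windows it runs from 54 − 51 = 3 to 58 − 47 = 11 days.

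**Step 5: the start of the Week 7 recording.** Section 6.1.2 puts the 24 hours after the Day 49 morning dose. The first sentence of 8.1.2, read literally, puts them before it. Section 4.8.12 has the device started in clinic ahead of that dose, and 8.1.2 itself later speaks of starting in clinic, so a workable start can be found. The two statements still disagree.

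**The case against.** The strongest reply is that the sentence is an editorial leftover. Sites work from the procedure list, and that list, the schedule footnotes, 8.1.2 and the endpoint all point the same way. The mix of weeks is disclosed, and the endpoint has been renamed, so a Week 8 session is arguably what end of treatment now means. For case A, Week 8 was the scheduled session; for case C, the rule picks correctly. The endpoint is secondary, supportive and not adjusted for multiplicity.

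Most of this stands, and it limits the size of the point. It does not remove it. The renaming was justified by enrolment under different protocol versions, not by a preference for Week 8 over a valid Week 7 recording. A secondary endpoint still needs a rule that says which of two valid recordings counts.

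A reader might also infer more than the documents support:

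- **That every subject is told to record at Week 8.** The bullet in the same section says otherwise. This is a contradiction, not a clear instruction.
- **That a Week 8 recording biases BID against QD dosing because treatment is ending.** The visit days are consistent with a last dose at about Day 56 (59 − 56 = 3; 84 − 56 = 28; 70 − 56 = 14). No passage says that the Day 56 evening dose is omitted, and the documents give no figure for loss of effect. The ABPM estimand compares each dose with placebo, and the planned comparison of 100 mg QD with 25 mg BID (SAP 6.4.3.2) uses change in SBP at Week 8, not ABPM.
- **That the ACTH stimulation test at Visit 14 disturbs the recording.** The test can be waived, Appendix 12.7 describes it for selected patients, it is scheduled alike in all arms, and nothing in the documents says that it affects ABPM.

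**Conclusion.** Wrong as written, and narrow. The visit instruction contradicts itself, and the SAP rule turns that contradiction into a possible replacement of valid endpoint-week data. The conclusion rests only on the wording of the two documents.

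The size cannot be given. The documents do not say whether any subject has valid sessions at both weeks, or how far the two would differ. The share of subjects recorded at Week 8 under the earlier schedule is not a measure of it, because those recordings were on schedule and would stay in the analysis. No sample size, power or alpha figure is affected.

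**What to change.** 1. **Protocol.** Reconcile the first sentence of 4.8.13 with its own bullet and with 3.2.2, 4.8.12 and 8.1.2. Reconcile 6.1.2 with the first sentence of 8.1.2 on when the Week 7 recording starts relative to the morning dose.
2. **SAP 6.4.2.1.** For subjects on the Week 7 schedule, define EOT as the Week 7 session unless it was deemed a failure, and then use the Week 8 repeat. Keep Week 8 for subjects under the earlier schedule. State how failure is identified in the data, since QC status is not used for selection.
3. **Optional.** List the study week of each EOT session by arm, and repeat the ABPM ANCOVA on Week 7 sessions for the arms that continued after Amendment 4.

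The cost is protocol wording, one derivation rule and, if item 3 is taken up, one listing and one table. No new data are needed. If recording is already complete, item 2 is the part that still matters, and it should be settled while the analysis team is blinded. The drawback of item 3 is that the two 12.5 mg arms (about 40 of the 160 Part 1 subjects) closed with Amendment 4. They would have little or no Week 7 data and cannot be included.
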